### 3.2.2 During the 6-Week at Home Clinical Trial

1. Parent/legal guardian will be asked to complete the questionnaire 2x daily for 45 days.
  - Once in the evening when applying the fresh night pant
  - Once in the morning when removing the used pant
2. In the evenings they will be asked to apply a fresh pant and wait ~15 minutes, before doing images, [REDACTED] and skin assessments. In the mornings, they will be asked to take the images before they remove the pant and then remove the pant to do skin assessments. [REDACTED]  
[REDACTED]
3. [REDACTED] the questionnaire has several questions to check compliance and ADEs and AEs throughout the clinical trial [REDACTED]  
[REDACTED]
4. Parent/ legal guardian will be asked to [REDACTED] assess skin [REDACTED] rash, [REDACTED], enter pant wear time and weight, assess leaking, and take images of the pant fit on the child in standing position. If the overnight pant did leak, they will be asked to take an image of the wet stain on the pajama pant in the crotch area as well as front, back or sides in a standing position, so we can see the location and size of the leak.
5. [REDACTED]  
[REDACTED]  
[REDACTED]
6. [REDACTED]  
[REDACTED]  
[REDACTED]
7. [REDACTED]  
[REDACTED]  
[REDACTED]
8. The parent/legal guardian will be called via phone or video chat after the 2 practice days to provide feedback after monitoring their data. Throughout the

clinical trial the submitted data will be monitored and subjects will be contacted at least once per week (either during planned study visits or remote phone/video calls) so the study site can give feedback, check on progress, track lot codes of new purchased products and answer questions throughout the clinical trial.

[REDACTED]

9. The following topics will be assessed by the site or sponsor based on the [REDACTED] responses and will be discussed during the weekly phone calls:
  1. Resolution/Tracking of any AEs or ADEs
  2. Resolution/Tracking of Medication Use
  3. Feedback on data quality and study progress
  4. Compliance (reasons for missed questionnaires or study instructions not being followed)
  5. [REDACTED]
  6. Track lot codes of new purchased own products
  7. Answer questions the subjects may have

### **3.2.3. Visit 2 – Return / Pick-up of Test Products After 3 Weeks (on Site)**

1. Parent/legal guardian will be asked to return to the test site to either return the unused test product or to pick up the test product for the final 3 weeks of the clinical trial, depending on their randomization.
2. [REDACTED]
3. [REDACTED].
4. Parent/legal guardian will be instructed on use of the test product or own product for the next 3 weeks.
5. Parent/legal guardian will be asked to complete [REDACTED] an after-product use feedback questionnaire after the first 3 weeks of the trial. Part of the questions is to be completed by the parent/legal guardian and part of the questions is to be completed by the child with the help of the parent/legal guardian.

### **3.2.4. Visit 3 – Return of Study Supplies and Close Out Visit**

1. Parent/legal guardian will be asked to return to the test site for the final visit.
2. The following will be resolved and recorded by clinical personnel:
  1. Subject Accountability
  2. Resolution/Tracking of any ADEs and AEs

3. Resolution/Tracking of any Medications Used  
Document lot codes of any new purchased own products
4. Return of instruments (balance, [REDACTED]  
[REDACTED])
5. Return of unused test pants (if applicable)
  
3. Parent/legal guardian will be asked to complete [REDACTED] an after-product use feedback questionnaire after the last 3 weeks of the trial. Part of the questions is to be completed by the parent/legal guardian and part of the questions is to be completed by the child with the help of the parent/legal guardian.
  
4. Subjects will be released from clinical trial and be allowed to go back to their normal habits.
  
5. Compensation details will be provided to parent/legal guardian. Payment will occur after all equipment is returned and verified by clinical personnel. Any damaged equipment should be returned to the site for safe disposal. Subjects will not be charged for equipment that was unintentionally broken or lost. At the completion of this visit, the subject will have completed the clinical trial.

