## 2. Objectives

The primary objective of this clinical trial is to confirm the in-use tolerability of the Ninjama EU overnight pant product, in the target population of bedwetters aged 4-7 years, based on a body of evidence from clinical assessments of skin, adverse events and parent/child perception data. This data will be part of the clinical evidence in the Clinical Evaluation Report needed to market this product as a Class 1 Medical Device in the EU, confirming that the product is safe to use and performs within its intended purpose.

The secondary objective is to understand the clinical benefit of the NJ EU overnight pant product in a bedwetting population aged 4-7 years, based on [REDACTED] waking up in a dry bed, via collecting H&P and parent/child perception data in diaries and end-of-use questionnaires.

[REDACTED]

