## 3.5 Subject Accountability

A Subject Accountability form will be completed at visit 3 for all subjects enrolled into the clinical trial.

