### **3.5.2 Replacement of Subjects**

If a subject drops out of the clinical trial, they will not be replaced, due to the short duration of the clinical trial.

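### The after-use parent/child questionnaire is not offered at early withdrawal, so a child who stops because of a product has no after-use rating of that product

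*Combined protocol and SAP*

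**What the plan says.** - **Timing of the questionnaire.** Section 3.2.3 (Visit 2) asks for "an after-product use feedback questionnaire after the first 3 weeks of the trial". Section 3.2.4 (Visit 3) asks for "an after-product use feedback questionnaire after the last 3 weeks of the trial". At both visits the child answers too: "part of the questions is to be completed by the child with the help of the parent/legal guardian".
- **Objectives (section 2).** Tolerability, the primary objective, is judged "based on a body of evidence from clinical assessments of skin, adverse events and parent/child perception data", with no instrument named. The secondary objective, clinical benefit, is pursued "via collecting H&P and parent/child perception data in diaries and end-of-use questionnaires".
- **Withdrawal.** Section 3.5.1 lets a child leave at any time, asks for the reason and records it in Subject Accountability. Section 7.5.1 has discontinuation filed with the sponsor within 72 hours. Section 3.5 says: "A Subject Accountability form will be completed at visit 3 for all subjects enrolled into the clinical trial". Section 3.5.2 adds: "If a subject drops out of the clinical trial, they will not be replaced".
- **Daily data.** Section 3.2.2 states: "Parent/legal guardian will be asked to complete the questionnaire 2x daily for 45 days". Rash grading and the child's irritation answer belong to these home assessments (sections 3.1, 3.3.4, 3.7.7 and 3.7.8). They are items 6 and 10 of the SAP (Attachment B).
- **Missing data.** The visible SAP rule excludes ratings recorded as not assessable and leaves the handling of non-evaluable observations to be documented before analysis. No rule for children who withdraw is visible.

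**The concern.** The plan foresees children stopping because they are uncomfortable, yet the after-use questionnaire is worded for families who have come to the end of a 3-week period. A child who leaves midway because of a product gives no after-use rating of it. Among the missing ratings, those of children who leave for that reason are the most likely to be unfavourable, so the summary for that product is drawn from children who stayed with it.

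The cross-over design adds a second effect. A child who stops on the test pant in period 2 has already rated the own product at Visit 2. The two product summaries then cover different children, and a within-child comparison loses that child altogether. No analysis set can supply a rating that was never requested.

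**Working it through.** The plan states no figure that depends on this point, and section 4.2 says the sample size was set on practical grounds. There is nothing to reproduce, so the check has two parts.

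**1. What a withdrawn child does and does not contribute**

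Inputs: two questionnaires a day for 45 days, with days 1 and 2 not evaluable (sections 3.2.1 and 3.2.2).

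- Full participation: 45 × 2 = 90 daily questionnaires, of which (45 − 2) × 2 = 86 are evaluable, against 2 after-use questionnaires.
- Stopping in period 1 on day d leaves up to (d − 2) × 2 evaluable daily questionnaires: 10 for d = 7, 24 for d = 14, 36 for d = 20. The child's irritation question is tied to pant removal, so that item may have fewer answers.
- After-use questionnaires: none for a child who stops in period 1; one, for the first product only, for a child who stops in period 2.

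The missing piece is the after-use questionnaire for the product in use at stopping, plus everything from any later period.

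**2. Illustration of the effect on the questionnaire**

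Input from the documents: about 32 children (Protocol Amendment 1, revised section 3.1). Assumptions, because the documents give no rates: k children stop because of the test pant before its questionnaire, each would have rated it unfavourably, nobody else leaves, and no completer complains. The questionnaire as planned shows 0/(32 − k). If every family that stopped also answered, it would show k/32. Intervals are exact (Clopper-Pearson) 95%.

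| k | As planned | Upper 95% limit | With a rating at stopping | 95% interval |
|---|---|---|---|---|
| 1 | 0/31 | 11.2% | 1/32 = 3.1% | 0.1 to 16.2% |
| 2 | 0/30 | 11.6% | 2/32 = 6.25% | 0.8 to 20.8% |
| 3 | 0/29 | 11.9% | 3/32 = 9.4% | 2.0 to 25.0% |
| 4 | 0/28 | 12.3% | 4/32 = 12.5% | 3.5 to 29.0% |

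If instead 6 of 32 families would rate the pant unfavourably (18.8%) and w of those 6 leave first, the observed share is (6 − w)/(32 − w): 5/31 = 16.1%, 4/30 = 13.3% and 3/29 = 10.3% for w = 1, 2 and 3. Both sets of numbers describe this questionnaire alone and leave out the diary and the recorded reasons.

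**The case against.** A reader might infer that a child who stops is absent from the perception data supporting tolerability. The documents do not support that. Rash and irritation are rated at home day by day up to stopping and are SAP endpoints, and the ITT set used for safety takes in every child who had the assigned product applied. The questionnaire itself is named only under the secondary objective.

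A reader might also infer that withdrawal leaves no trace, or that a withdrawn child cannot reach Visit 3. Neither follows. The reason is recorded, discontinuation is filed within 72 hours, and the accountability form is required for everyone enrolled. The plan does not say whether a family that stops attends the close-out visit early; it may well do so to return equipment. Nor does the rule in section 7.5.1 that keeps most pant-area rash out of adverse event reporting leave rash at stopping unknown, since the last diary entry would normally show it.

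The illustration rests on invented rates, and even its largest shift, from 18.8% to 10.3%, lies inside the exact 95% interval for 6/32 (7.2% to 36.4%). Redaction also hides several SAP endpoints and one schedule row marked at Visits 2 and 3, so how the questionnaire is analysed cannot be seen.

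All of this narrows the point without removing it. Diary entries and a withdrawal reason are not answers to the after-use questionnaire and cannot be tabulated with completers' answers. If an early Visit 3 is intended, the questionnaire's timing does not provide for it. Sampling error does not offset a loss that, for product-related stops, would tend to run in one direction.

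**Conclusion.** The point holds in a limited form. The plan has no administration of the after-use questionnaire at early withdrawal, so a child who stops because of a product is lost from that instrument for that product. This can make the end-of-use perception data look more favourable. It bears on the secondary objective directly and on the primary one only through the general reference to perception data. A broader claim, that the tolerability evidence as a whole is biased, is not supported, because the daily ratings and the withdrawal reason remain.

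The size of the bias is unknown. Its direction rests on the assumption that families who leave because of a product would rate it poorly; departures for other reasons, such as the burden of daily measurements, have no clear direction. With about 32 children and no replacement, one or two such departures would be visible in the questionnaire summary, and the ratings cannot be recovered afterwards. That makes this a worthwhile low-cost improvement rather than a flaw that undermines the trial.

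**What to change.** In section 3.5.1, with a matching footnote to the schedule in 3.2.5, state that a family stopping early is asked, if willing, to complete two existing forms at stopping or at equipment return: the after-use questionnaire for the product in use, and the Subject Accountability form. Where no visit is possible, this can be done by phone or through the digital questionnaire already in use. Align section 3.5 so that the accountability form is not tied to Visit 3 for these children.

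In Attachment B, add that such a questionnaire is summarised with the others under that product and flagged as an early stop, so that the summary can be read with and without it.

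The cost is one sentence, one footnote and one SAP line, with no new form and a few extra minutes for the families concerned. Some will decline, so the gap will shrink rather than close, and early-stop ratings will reflect shorter use than completers' ratings. The flag is there for that reason.

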### 3.2.5. Clinical Trial Schedule of Events

Procedure	Visit 1: Enrollment and Training	Visit 2: Product pick up and instrument check (3 weeks after visit 1)	AT HOME: Clinical Trial Mode Days 1 – 45	Weekly Phone Calls (after 2 days and then weekly, if no study visits planned for that week)	Visit 3: Final Visit
Informed Consent	X				
Demographics	X				
Inclusion/Exclusion	X				
Anthropometry	X				
Subject Instructions (training session)	X				
H&P Questionnaire [REDACTED]	X				
Randomization	X				
Product Distribution (per randomization)	X	X			
Compliance/ AE Resolution		X	X	X	X
Twice Daily Questionnaire [REDACTED] (photos and measurements)			X		
[REDACTED]		X			X
Subject Accountability					X

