## 3. Investigational Plan

### 3.1 Clinical Trial Design

This will be a single center, single blinded (sponsor's team will be blinded to the product codes), randomized, cross-over, IRB-Approved, in-home clinical test design over 6 weeks, with two usage periods of 3 weeks each. During one period the child will maintain usage of their usual absorbent night pant/diaper and during the other usage period they will use the NJ EU absorbent pant. We will track habits and practices that may impact skin health and product performance as well as medication use and Adverse Events/ Adverse Device Effects (AEs /ADEs). Children will be asked to wear either their own pants or the test pants exclusively at night and parent/legal guardian will be asked to collect data in the evening before bed and in the mornings after getting up.

Parent/Legal Guardian will be trained to execute the measurements on their own child for the following reasons:

1. Children this age are usually told not to let strangers touch them in the genital and buttock area, so we want to avoid telling kids it is OK in this case. We will ensure that the child is comfortable to participate in this clinical trial and can at any time end their participation in this clinical trial should they feel uncomfortable.
2. Due to COVID restrictions, clinical trial personnel should minimize close contact with panelists as much as possible, especially with children under 5 years of age, who cannot be vaccinated. We will therefore ask the trained parent/legal guardian to do the measurements on his/her own child/ren. Children can stop the study procedures at any time if/when they feel uncomfortable.

This clinical trial is designed to track the following:

- general safety (AEs and ADEs),  
[REDACTED]
- assess fit and performance of the overnight pant products (fit images, leaks, [REDACTED])

The following table shows which endpoints will be measured at which time and where on the child:

Endpoint	When Measured	Where Measured
Leaking & Pant Fit	Before pant removal	Waist front and back, crotch area, leg cuffs
Child skin irritation perception	Directly before removing pant	Entire pant area
AE, ADE, [REDACTED]	Observed all the time and reported twice a day	Observe child and pant

[REDACTED] Leaking and Pant Fit: Mobile phone images of the pant on the child will be collected by the parent/legal guardian at home [REDACTED]

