- Child Perception: Child will be asked simple yes/ no questions to determine if they feel irritation [REDACTED]. If yes, the parent/legal guardian will ask the child to point to location where they feel the irritation [REDACTED].

- [REDACTED]

- [REDACTED]

Up to 30 children (approximate split of 15 males and 15 females) who meet inclusion/exclusion criteria will be enrolled in the clinical trial. S7 children will be enrolled in this clinical trial because nocturnal enuresis is most prevalent in children aged 4-7 and the pant design for S7 and S8 products are similar. Therefore, the data generated for the S7 population can be used to support the S8 population. Children for this clinical trial will be enrolled by North Cliff Consultants in Cincinnati, USA. Eligible subjects will be bedwetters who have wet the bed at least once a week or more over the past 3 months. The children should be accustomed to wearing an absorbent pant product overnight. They will be asked to use their own overnight pant every night for 3 weeks of the clinical trial and will be asked to use the NJ EU test pant every night for the other 3 weeks of the clinical trial. The order of the NJ EU product and own product will be randomized. Parents will

be asked to refrain from using wet wipes to clean the child's skin for the duration of the clinical trial (no test wipes will be provided).

If a subject drops out of the clinical trial, they will not be replaced, due to the short duration of the clinical trial.

Once qualified, parent/legal guardian will be asked to pick up the equipment [REDACTED] [REDACTED] from North Cliff Consultants. They will receive training on how to handle the equipment and how to complete the questionnaires. Parent/legal guardian will be required to begin with the clinical trial after the training session. They will be given 2 days to practice [REDACTED] before data is officially collected for the clinical trial.

Parent/legal guardian will be instructed to complete a digital questionnaire twice daily (once in the morning before removing the used pant and once in the evening when applying the fresh pant) [REDACTED]. This will include taking four photos of the child wearing the pant (front, back and both hips) [REDACTED].

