7. The use of skin products like lotions, oils, powders, creams, sunscreens, wet wipes and moisturizing bubble baths will not be allowed to be used in the pant area and thighs, unless needed for medical reasons. Use of these skin preparations will be captured in the daily questionnaire [REDACTED]  
[REDACTED].
8. After enrollment, parent/legal guardian will receive the following items:  
[REDACTED]  
[REDACTED]
  - [REDACTED]
  - Two coin-cell batteries as back-up
  - [REDACTED])
  - Kitchen scale (balance) with USB charging cable
  - [REDACTED]
  - Measuring tape
  - [REDACTED]
  - Written subject instructions
9. Parent/ legal guardian will participate in a training session on the following:
  - a. Review of [REDACTED] questionnaire
  - b. How to take photos using mobile phone [REDACTED]
  - c. How to assess rash, imprints/marks on the skin
  - d. [REDACTED])
  - e. [REDACTED]
  - f. [REDACTED]
  - g. [REDACTED]
  - h. How to weigh the pant
10. [REDACTED]  
[REDACTED]
11. Parent/legal guardian will be asked to begin completing the questionnaire (2x/day) for 45 days. The first 2 days will be considered practice days and data from day 1 and 2 will be considered non-evaluable.

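### Visit 2 is timed from Visit 1, not from the end of the practice days, so period 1 yields about 19 evaluable nights instead of 21 and the two periods are unequal

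*Combined protocol and SAP*

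**What the plan says.** - **Design.** Section 3.1 sets out a crossover "with two usage periods of 3 weeks each".
- **Start.** Section 3.1 also says "Parent/legal guardian will be required to begin with the clinical trial after the training session". Randomization and product distribution are both marked at Visit 1 in 3.2.5, so the at-home phase opens on the period 1 product.
- **Practice days.** Section 3.2.1, item 11: "The first 2 days will be considered practice days and data from day 1 and 2 will be considered non-evaluable".
- **Diary length.** Section 3.2.2, item 1: "Parent/legal guardian will be asked to complete the questionnaire 2x daily for 45 days". The schedule column reads "AT HOME: Clinical Trial Mode Days 1 – 45", so the practice days lie inside the 45.
- **Product switch.** Section 3.2.5 heads the Visit 2 column "Product pick up and instrument check (3 weeks after visit 1".
- **Period 2.** Section 3.2.3, item 4: "Parent/legal guardian will be instructed on use of the test product or own product for the next 3 weeks". Section 3.2.4 also describes the second period as three weeks.
- **Visit 3.** No day or interval is given in 3.2.4 or 3.2.5, and neither visit has a window in the text reviewed.
- **Analysis.** The SAP (Attachment B) uses cumulative counts for parental rash and child irritation scores, with part of that text redacted. Leaks are a percentage of loaded pants. Period and carryover effects are to be evaluated, with means plotted by period.

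**The concern.** These statements cannot all be met. If the switch falls three weeks after Visit 1 and two of those days do not count, period 1 is shorter than three evaluable weeks. If the diary then runs its full 45 days, the nights lost from period 1 reappear in period 2.

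In a crossover, unequal observation time matters most for outcomes that accumulate. A child with the same nightly chance of rash throughout would collect more rash scores in the longer period. Plotted by period as totals, that looks like a period effect, which is what the SAP sets out to look for. Skin assessments also feed the primary tolerability objective in Section 2. A site reading the schedule literally has no other instruction to correct it.

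**Working it through.** **Inputs.** 45 diary days (3.2.1, 3.2.2, 3.2.5); 2 practice days (3.2.1); switch 21 days after Visit 1 (3.2.5); two periods of 21 nights (3.1). Assumption: Day 1 is the day of Visit 1, since 3.1 starts the trial after the training session.

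**Step 1. Reproduce the 45 days.** From the evening of Day 1 to the morning of Day 45 there are 45 - 1 = 44 nights. The stated design needs 2 + 21 + 21 = 44 nights. The diary length therefore fits two full evaluable periods after the practice days.

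**Step 2. Period 1 as scheduled.** The switch comes after 21 nights (Day 22). Evaluable nights = 21 - 2 = 19, which is 2/21 = 9.5% below the stated length.

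**Step 3. Period 2 as scheduled.** The documents support two readings:

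| Reading | Period 1 | Period 2 | Ratio |
|---|---|---|---|
| Period 2 is three weeks (3.2.3); use ends about Day 43 and the diary is not filled | 19 | 21 | 21/19 = 1.11 |
| Period 2 runs to Day 45 (3.2.2, 3.2.5) | 19 | 44 - 21 = 23 | 23/19 = 1.21 |

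**Step 4. Sensitivity.** With use to Day 45, a Visit 2 one day early gives 18 and 24 nights, and one day late gives 20 and 22. If the Day 3 morning record, which covers the second practice night, counts as evaluable, period 1 has 20 nights against 21 or 23. Counting nights as in Step 2, a switch after 23 nights (Day 24) gives 21 and 21.

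**Step 5. Effect on a raw count.** With a constant nightly rate r, the expected counts are 19r in period 1 and 21r or 23r in period 2. The rate cancels, leaving a 11% or 21% rise with no true period effect. A per-night rate or percentage shows none.

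**Step 6. Effect on the product comparison.** Let T and O be the nightly rates on test and own product, and take the 19/23 split.

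- Own-first children: expected difference 23T - 19O.
- Test-first children: expected difference 19T - 23O.
- Equally weighted average of the two sequence means: (42T - 42O)/2 = 21(T - O), whatever the number of children in each sequence. For 19/21 it is (40T - 40O)/2 = 20(T - O).

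An unadjusted pooled total does not cancel if the sequences finish unequal. For assumed splits of 30 completers:

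| Own-first / test-first | Period nights | Test nights | Own nights | Excess |
|---|---|---|---|---|
| 17 / 13 | 19/23 | 17×23 + 13×19 = 638 | 17×19 + 13×23 = 622 | 2.6% |
| 18 / 12 | 19/23 | 18×23 + 12×19 = 642 | 18×19 + 12×23 = 618 | 3.9% |
| 17 / 13 | 19/21 | 17×21 + 13×19 = 604 | 17×19 + 13×21 = 596 | 1.3% |
| 18 / 12 | 19/21 | 18×21 + 12×19 = 606 | 18×19 + 12×21 = 594 | 2.0% |

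With the planned 16/16 allocation (Amendment 1) and no dropout, exposure to the two products is equal.

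**The case against.** The best defence is that the Visit 2 header is only a nominal label. Section 3.1 presents the two practice days as coming before official data collection, and the 45 days fit that intent. This is probably what the sponsor meant. It stands as an account of intent, but the schedule and the title of 3.2.3 do not say it, and no visible text tells the site to wait two more days.

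Second, a reader might infer that the split is firmly 19 and 23. The documents do not settle that: 3.2.3 and 3.2.4 give period 2 three weeks, and Visit 3 has no stated day. Only the period 1 shortfall is independent of when period 2 ends.

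Third, the harm depends on how scores are counted. The rash and irritation items are partly redacted, so a denominator may exist there. The leak endpoint is already a percentage, and the by-period plots would show no artefact if the means are of nightly values. All of this stands, and it limits the effect to raw cumulative counts.

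Fourth, a reader might infer that the product comparison is biased unless the sequences finish equal. Step 6 shows otherwise for an estimate that weights the two sequences equally. Only an unadjusted pooled difference is exposed, by a few percent. The SAP names no model, so this protection is available but not assured.

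Finally, the contents list names a second amendment, and Amendment 1 cites an attachment on COVID or weather procedures. Neither was available here, and either could bear on visit timing.

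**Conclusion.** The point holds as an inconsistency in the schedule with a modest effect. Read as written, the plan does not deliver two evaluable periods of three weeks: period 1 has about 19 evaluable nights, and period 2 has 21 or 23. The Visit 2 timing is the element that does not fit, because the diary length matches two practice nights plus two full periods.

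A raw cumulative skin score would show a spurious period difference of roughly 11-21%. An unadjusted pooled product total would be out by about 1-4% under the sequence splits assumed above. The documents do not support a claim that the product comparison is materially biased, or that the leak result is affected to any important degree.

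These figures assume that Day 1 is the day of Visit 1, that Visit 2 falls exactly 21 days later, that the nightly rate is constant, and that no unseen text changes the timing. The correction is worth making because it is cheap and restores the stated design.

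**What to change.** Make the Visit 2 column header in 3.2.5 and the title and text of 3.2.3 agree with the practice days and the 45-day diary. The direct route is to time Visit 2 at three weeks after the end of the two practice days (23 nights after Visit 1, Day 24), state the day of Visit 3 (Day 45 on the same count), and give a window for each visit. Say also whether the Day 3 morning record counts.

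If the visit dates cannot move, put the correction in the SAP before the data are analysed: express cumulative rash and irritation scores per evaluable night, or use the same number of evaluable nights from each period. A sequence-balanced crossover estimate for the product difference would guard against unequal sequence sizes.

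The schedule change moves Visit 2 by two days and requires two more nights' supply for test-first children, within the existing 45 days. The SAP route costs only wording.
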